# 6.4 TREATMENT BREAKS

Treatment breaks must be clearly indicated in the treatment record along with the reason(s) for the treatment break(s). Treatment breaks, if necessary, should not exceed 3 treatment days at a time and 5 treatment days total. Treatment breaks should be allowed only for resolution of severe acute toxicity and/or for intercurrent illness and not for social or logistical reasons. Any treatment break(s) exceeding 2 treatment days for reasons other than toxicity/illness will be considered a protocol deviation.

## 6.5 DEVICE-SPECIFIC CONSIDERATIONS

Photon beams of  $\geq$  6MV are required with treatment distance  $\geq$  80 cm source to axis distance for isocentric techniques.

Immobilization: Treatment should include use of a thermoplastic head and shoulder mask.

**Planning CT scan:** CT scan thickness should be  $\leq 0.3$  cm. If possible, planning CT scan should be done with contrast. MRI and/or PET/CT should be fused to the planning CT scan.

**Localization:** Isocenter or reference point port localization images or volumetric imaging study on the linear accelerator couch should be obtained at each treatment on the treatment unit immediately before treatment to ensure proper alignment of the geometric center (i.e., isocenter) of the simulated fields.

# 6.5 DRUG THERAPY

There will be no concurrent chemotherapy. Other drug therapy (e.g. lidocaine rinses, skin creams, narcotics) as clinically indicated for the management of radiotherapy side effects as per standard of care.

# 7 STUDY PROCEDURES AND SCHEDULE

#### 7.1 STUDY PROCEDURES/EVALUATIONS

 $PSI = \frac{V_{diagnosis} \times e^{\lambda \Delta t} - V_{treatment}}{V_{diagnosis} \times (e^{\lambda \Delta t} - 1)}$ 

PSI will be calculated according the above formula, where Vdiagnosis is the volume of the tumor at first imaging and Vtreatment is the volume of the tumor at second pretreatment imaging, t is time, and  $\lambda$  is doubling time. Each site of disease will be contoured individually, and PSI calculated. PSI of lymph nodes will have priority over primary site. PSI of the largest lymph node will have priority over smaller lymph nodes. Patients with a PSI  $\leq$  0.75 will be assigned to conventional fractionation group, and PSI > 0.75 will be assigned to the hyperfractionation group (Figure 3).

- Medical history within 90 days of start of treatment, including history, focused physical exam of the head and neck, assessment of performance status, and weight.
- Imaging will consist of pre-treatment CT and/or MRI, with at least 2 exams one week apart. Pre-treatment PET/CT while ideal, is not required. On first day of RT (or within 5 days of starting RT), CT simulation will be repeated. During week 4 of radiotherapy (~fraction 20 for conventionally fractionated patients or ~fraction 40 for hyperfractionation patients, CT simulation and MRI will be repeated. At ~8 weeks after treatment is complete CT of neck or ~12 weeks PET/CT will be performed for response assessment.

# 7.2 CORRELATIVE STUDY PROCEDURES/EVALUATIONS

The following samples will be sent to the Moffitt Cancer Center Tissue Core for processing and storage for the following analyses in the [name] Laboratory. Detailed sample collection and processing are described in Lab Manual.

#### 7.2.1 EVALUATION OF TUMOR IMMUNE MICROENVIRONMENT (TIM)

An innovative methodology, multiplex immunohistochemical (mIHC) staining, developed in the [name] Laboratory allows the analysis of an array of markers from limited sample specimens. The evaluation of a complex cellular microenvironment is best accomplished using high mIHC, which enables simultaneous detection and measurement of multiple protein antigens on the same tissue section allowing accurate classification of cells as well as enumeration and quantification of protein signal. This is accomplished by using sequential steps of antigen retrieval followed by primary antibody application, and then antibody stripping. The process is repeated using different primary antibodies for each antibody target. The result is that up to 18 protein targets can be visualized along with the nuclear stain. This complex staining can then be analyzed by imaging systems such as the the Aperio FL scanning system. Image analysis software such as Cell Profiler can then be applied to enumerate cells and quantify signal. Complex analysis can determine cellular densities and also measure co-localized targets. The multiplexing will encompass evaluation of antigen presenting cells, T cells, natural killer cells, B cells, and tumor cells using 30 immune cell markers and EGFR. The goal is to link a comprehensive clinical characterization and immune microenvironment assessment and to correlate these with radiation treatment response and survival.

#### 7.2.2 EVALUATION OF HPV DNA VIRAL LOAD IN ORAL GARGLES AND PLASMA

HPV genotype and viral load will be determined on oral gargle and plasma specimens collected before, during, and after treatments using the most updated assay at the time of analyses.

#### 7.2.3 TUMOR SAMPLE SUBMISSION

Formalin-fixed paraffin-embedded (FFPE) tumor tissue samples will be collected at pre-treatment (MANDATORY). The FFPE tumor could be any archived tissue obtained before starting radiation therapy. The tumor tissue samples will be submitted to the Moffitt Tissue Core for cataloging and storage until the analyses at the [name]'s laboratory.

An FFPE tumor block or 10, 4 micron unstained slides should be submitted with the submission form. A Pathology Report and one hematoxylin and eosin-stained slide documenting that the submitted block or slides contain tumor should also be submitted with the tissue. The report and hematoxylin and eosin-stained slide must include the protocol number and patient's case number. The patient's name and/or other identifying information should be removed from the report. The surgical pathology numbers and information must NOT be removed from the report. If the subject has multiple archival samples available, samples from various settings may be requested.

#### 7.2.4 ORAL GARGLE SAMPLE SUBMISSION AND PROCESSING

Collection Notification Form (CNF) for each oral gargle and each blood sample will be email to Tissue Core Acquisition and Tissue Core SPL groups 24 hours before collection.

#### **Collection sites:**

Moffitt Cancer Center

Oral gargle specimens will be collected using 15 ml of a locally available mouthwash.

#### **Clinical events:**

- 1. Pre-therapy
- 2. During treatment at 1 weeks (+/- 3 days)
- 3. During treatment at 2 weeks (+/- 3 days)
- 4. During treatment at 3 weeks (+/- 3 days)
- 5. During treatment at 4 weeks (+/- 3 days)
- 6. End of the treatment (+/- 3 days)
- 7. 3 months after the treatment (+/- 14 days)
- 8. 6 months after the treatment (+/- 14 days)
- 9. 12 months after the treatment (+/- 14 days)
- 10. 18 months after the treatment (+/- 14 days)
- 11. 24 months after the treatment (+/- 14 days)
- 12. Time of disease progression if sooner than 24 months
- 13. End of study if the patient is off the study before 24 months with any reasons.

# Procedures: The oral gargle samples should be processed within 24 h from collection. Oral gargle processing: Refer to Lab Manual.

#### 7.2.5 BLOOD SAMPLE SUBMISSION AND PROCESSING

Collection Notification Form (CNF) for each blood sample will be email to Tissue Core Acquisition and Tissue Core SPL groups 24 hours before collection.

## **Collection sites:**

Moffitt Cancer Center

1x 10 ml Lavender EDTA tube of blood and 1x 10ml LBgard blood tube will be collected from each clinical event.

## **Clinical events:**

- 1. Pre-therapy
- 2. During treatment at 2 weeks (+/- 3 days)
- 3. During treatment at 4 weeks (+/- 3 days)
- 4. End of the treatment (+/- 3 days)
- 5. 3 months after the treatment (+/- 14 days)
- 6. 6 months after the treatment (+/- 14 days)
- 7. 12 months after the treatment (+/- 14 days)
- 8. 18 months after the treatment (+/- 14 days)
- 9. 24 months after the treatment (+/- 14 days)
- 10. Time of disease progression if sooner than 24 months
- 11. End of study if the patient is off the study before 24 months with any reasons.

#### Procedures: The blood samples should be processed within 2 h from collection.

#### Plasma processing: Refer to Lab Manual.

Specimens taken from patient:	Collected when:	Submitted as:
A paraffin- embeddedtissue of archival tissue taken before initiation of treatment	Pre-treatment	Paraffin-embedded tissue block, or 10,4 micron unstained slides (minimum of 10 unstained slides) Refer to Lab Manual for processing and storage
ORAL GARGLE: Collected using 15 ml of a locally available mouthwash.	
 
Pre-therapy
 
During treatment at 1 weeks (+/- 3days)
 
During treatment at 2 weeks (+/- 3days)
 
During treatment at 3 weeks (+/- 3days)
 
During treatment at 4 weeks (+/- 3days)
 
End of the treatment (+/- 3 days)
 
End of the treatment (+/- 14 days)
 
6 months after the treatment (+/- 14 days)
 
8 6 months after the treatment (+/- 14 days)
 
9 12 months after the treatment (+/- 14 days)
 
10 18 months after the treatment (+/- 14days)
 
11 24 months after the treatment (+/- 14days)
 
12. Time of disease progression if sooner than 24 months
 
13. End of study if the patient is off the study before 24 months with anyreasons.
 
	Refer to Lab Manual for Processing and storage
PLASMA: 1x 10 mL of anticoagulated wholeblood in EDTA tube (purple/ lavender top).	
 
Pre-therapy
 
During treatment at 2 weeks (+/- 3days)
 
During treatment at 4 weeks (+/- 3days)
 
	Refer to Lab Manual for processing and storage

# Specimen collection summary for correlative studies

Specimens taken from patient:	Collected when:	Submitted as:
1x 10 mL of anticoagulated wholeblood in LBgard blood tube.	
 
End of the treatment (+/- 3 days)
 
3 months after the treatment (+/- 14days)
 
6 months after the treatment (+/- 14days)
 
7. 12 months after the treatment (+/- 14days)
 
8. 18 months after the treatment (+/- 14days)
 
9. 24 months after the treatment (+/- 14days)
 
10. Time of disease progression if sooner than 24 months
 
11. End of study if the patient is off the study before 24 months with anyreasons.
 
	Refer to Lab Manual for Processing and storage
PBMC: 1x10 mL of nticoagulated whole blood in EDTA tube (purple/ lavender top).	
 
Pre-therapy
 
During treatment at 2 weeks (+/- 3days)
 
During treatment at 4 weeks (+/- 3days)
 
End of the treatment (+/- 3 days)
 
3 months after the treatment (+/- 14days)
 
6 months after the treatment (+/- 14days)
 
12 months after the treatment (+/- 14days)
 
18 months after the treatment (+/- 14days)
 
24 months after the treatment (+/- 14days)
 
Time of disease progression if sooner than 24 months
 
End of study if the patient is off the study before 24 months with anyreasons.
 
	Refer to Lab Manual for Processing and storage

# 7.3 STUDY SCHEDULE

		On Treatment					
Assessments	Pre-Study (within 90 d. of Tx start)	First day, prior to RT (within5 days prior)	Once-a- WeekDuring RT	Week 4 During RT	End of Tx (+/- 3 days)		
Evaluations							
Rad Onc EvalH&P, ECOG, Weight	х		Х				
Imaging							
CT# or MRI of primary and neck a,b	Xh	Х		х			
PET/CT	Xc						
Labs							
Urine PregnancyTest (only Females of Child bearing potential)	х						
Tumor Tissue for RSI	Х						
Oral Gargle for HPV e	Х		х	х	х		
Plasma for HPV f	Х		Х	Х	Х		

	From End of Treatment							
Assessments	4 Wks +/- 14 days	2-3 mo +/- 14 days d	6 mo +/- 14 days	12 mo +/- 14 days	18 mo +/- 14 days	24 mo +/- 14 days	Time of disease progression if sooner than 24 mos g	End of study if the patient is off the study before 24 mos with any reasons g
Evaluations								
Rad Onc Eval H&P, ECOG, Weight	х	х	х	Х				

Assessments	4 Wks +/- 14 days	2-3 mo +/- 14 days d	6 mo +/- 14 days	12 mo +/- 14 days	18 mo +/- 14 days	24 mo +/- 14 days	Time of disease progression if sooner than 24 mos g	End of study if the patient is off the study before 24 mos with any reasons g
Imaging								
CT# or MRI of primary and neck a,b		Xc						
PET/CT		Xc						
Labs								
Urine PregnancyTest (only Females of Child bearing potential)								
Tumor Tissue for RSI								
Oral Gargle for HPV e		х	х	х	х	Х	х	Х
Plasma for HPV f		Х	Х	Х	Х	Х	Х	Х

aInterim MRI or CT for response assessment.

bCT at day 1 and week 4 may be done using Department of Radiation Oncology CT SimulationcAt physician discretion. Pre-treatment PET/CT can be up to 180 days prior to CT simulation. dA CT at 2 months and/or PET/CT at 3 months may be done at physician discretion.

eOral Gargle for HPV to be collected at pre-therapy, during treatment at week 1, week 2, week 3, week 4, end of treatment, 3 months post-RT, 6 months post-RT, 12 months post-RT, 18 months post-RT, 24 months post-RT, time of diseaseprogression (if sooner than 24 months), and end of study (if patient discontinues the study with any reason sooner than 24 months). See 7.2.4/7.2.5 for collection windows.

fBlood samples to be collected at pre-therapy, during treatment at week 2 and week 4, end of treatment, 3 months post-RT, 6 months post-RT, 12 months post-RT, 18 months post-RT, 24 months post-RT, time of diseaseprogression (if sooner than 24 months), and end of study (if patient discontinues the study with any reason sooner than 24 months). See 7.2.4/7.2.5 for collection windows.

gFollowing this visit, patients are considered off the trial and are followed as per standard of care. hPre-treatment CT or MRI for PSI calculation can be up to 180 days prior to CT simulation.

# 7.4 CONCOMITANT MEDICATIONS, TREATMENTS, AND PROCEDURES

# Not applicable

# 7.5 PROHIBITED MEDICATIONS, TREATMENTS, AND PROCEDURES

Not applicable

# 7.6 PROPHYLACTIC MEDICATIONS, TREATMENTS, AND PROCEDURES

#### Not applicable

## 8 ASSESSMENT OF SAFETY

## 8.1 SPECIFICATION OF SAFETY PARAMETERS

#### 8.1. DEFINITION OF ADVERSE EVENTS

Adverse event means any untoward medical occurrence associated with the use of an intervention in humans, whether or not considered intervention-related (21 CFR 312.32 (a)).

#### 8.1.2 DEFINITION OF SERIOUS ADVERSE EVENTS

Adverse events and suspected adverse reactions are considered "serious" if, in the view of either the investigator or sponsor, they result in any of the following outcomes: death, a life-threatening adverse event, inpatient hospitalization or prolongation of existing hospitalization, a persistent or significant incapacity or substantial disruption of the ability to conduct normal life functions, or a congenital anomaly/birth defect. Important medical events that may not result in death, be life-threatening, or require hospitalization may be considered serious when, based upon appropriate medical judgment, they may jeopardize the patient or subject and may require medical or surgical intervention to prevent one of the outcomes listed in this definition. Examples of such medical events include allergic bronchospasm requiring intensive treatment in an emergency room or at home, blood dyscrasias or convulsions that do not result in inpatient hospitalization, or drug abuse.

#### 8.1.3 DEFINITION OF UNANTICIPATED PROBLEMS

OHRP considers unanticipated problems (UPs) involving risks to participants or others to include, in general, any incident, experience, or outcome that meets all of the following criteria:

- Unexpected in terms of nature, severity, or frequency given (a) the research procedures that are described in the protocol-related documents, such as the IRB-approved research protocol and informed consent document; and (b) the characteristics of the participant population being studied;
- Related or possibly related to participation in the research ("possibly related" means there is a reasonable possibility that the incident, experience, or outcome may have been caused by the procedures involved in the research); and
- Suggests that the research places participants or others at a greater risk of harm (including physical, psychological, economic, or social harm) than was previously known or recognized.

This study will use the OHRP definition of UP.

#### 8.2 CLASSIFICATION OF AN ADVERSE EVENT

## 8.2. SEVERITY OF

All AEs will be graded using the CTCAE 5 criteria. For AEs not included in the protocol-defined grading system, the following guidelines will be used to describe severity.

- **Mild** Events require minimal or no treatment and do not interfere with the participant's daily activities.
- Moderate Events result in a low level of inconvenience or concern with the therapeutic measures. Moderate events may cause some interference with functioning.
- Severe Events interrupt a participant's usual daily activity and may require systemic drug therapy or other treatment. Severe events are usually potentially lifethreatening or incapacitating.]>

# 8.2.2 RELATIONSHIP TO STUDY AGENT

The clinician's assessment of an AE's relationship to the study agent (drug, biologic, device) is part of the documentation process, but it is not a factor in determining what is or is not reported in the study. If there is any doubt as to whether a clinical observation is an AE, the event should be reported. All AEs must have their relationship to study agent assessed. In a clinical trial, the study product must always be suspect. To help assess, the following guidelines are used.

- Attribution of the AE:
  - Definite The AE is clearly related to the study treatment.
  - Probable The AE is likely related to the study treatment.
  - Possible The AE may be related to the study treatment.
  - Unlikely The AE is doubtfully related to the study treatment.
  - Unrelated The AE is clearly NOT related to the study treatment.

# 8.3 TIME PERIOD AND FREQUENCY FOR EVENT ASSESSMENT AND FOLLOW-UP

The occurrence of an AE or SAE may come to the attention of study personnel during study visits and interviews with study participants presenting for medical care, or upon review by a study monitor. All AEs, including local and systemic reactions not meeting the criteria for SAEs, will be captured on the appropriate CRF. Information to be collected includes event description, time of onset, clinician's assessment of severity, relationship to study product (assessed only by those with the training and authority to make a diagnosis), and time of resolution/stabilization of event. All AEs occurring during the study must be documented appropriately, regardless of relationship. All AEs will be followed to adequate resolution.

Any medical condition that is present at the time that the participant is screened will be considered as baseline and not reported as an AE. However, if the study participant's condition deteriorates at any time during the study, it will be recorded as an AE. UPs will be recorded in the data collection system throughout the study.

Changes in the severity of AEs will be documented to allow an assessment of the duration of the event at each level of severity to be performed. AEs characterized as intermittent require documentation of onset and duration of each episode.

The PI will record all reportable events with start dates occurring any time after informed consent is obtained until 7 (for non-serious AEs) or 30 days (for SAEs) after the last day of study participation. At each study visit, the investigator will inquire about the occurrence of AE/SAEs since the last visit. Events will be followed for outcome information until resolution orstabilization are achieved.

All Grade 3 or greater AEs will be monitored until resolution or, if the AE is determined to be chronic, a cause is identified. If an AE is considered potentially related to study treatment and remains ongoing at the conclusion of the study, the event will be followed until resolution, stabilization, or initiation of treatment that confounds the ability to assess the event. RT-related AEs and SAEs will be collected at follow-up contact 90 days from the end of treatment provided no new treatments have been initiated that could confound the ability to assess the event.

# 8.4 **REPORTING PROCEDURES**

# 8.4. ADVERSE EVENT

All Grade 3 or greater Adverse Events possibly, probably, or definitely related to radiotherapy up to the primary outcome time point (4 weeks) **MUST** be reported in routine study data submissions. Data will be captured in Oncore, Moffitt Cancer Center's clinical trials database. Regulatory documents and case report forms will be monitored internally according to Moffitt Cancer Center Monitoring Policies.

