# 8.4.2 SERIOUS ADVERSE EVENT REPORTING

Any clinical adverse event or abnormal laboratory test value that meets the definition of serious noted below and occurs in a patient during the course of the study, irrespective of the treatment received by the patient, must be reported within 24 hours of the investigator becoming aware of the occurrence. Serious adverse event definition and reporting requirements will be in accordance with the International Conference of Harmonisation (ICH) Guideline for Clinical Safety Data Managements.

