# Definitions and Standards for Expedited Reporting, Topic E2A:

An SAE is defined as any untoward medical occurrence that at any dose:

1. Results in death

2. Is immediately life-threatening (i.e., in the opinion of the investigator, the AE places the patient at immediate risk of death; it does not include a reaction that, had it occurred in a more severe form, might have caused death)

- 3. Requires inpatient hospitalization or results in prolongation of an existing hospitalization
- 4. Results in persistent or significant disability or incapacity
- 5. Is a congenital anomaly or birth defect

6. Is an important medical event that may not be immediately life-threatening, result in death, or require hospitalization, but may be considered an SAE when, based upon appropriate medical judgment, it jeopardizes the patient or may require medical or surgical intervention to prevent one of the outcomes listed above.

Any SAE, whether or not considered to be related to study treatment, will be reported within 24 hours of the investigator becoming aware of the event. It will be recorded on both the SAE form and the CRF AE page. Additional SAE information including medications or other therapeutic measures

used to treat the event, action taken with the study drug due to the event, and the outcome / resolution of the event will be recorded on the SAE form. Forms for reporting SAEs will be provided to the study sites.

Conversely, some hospitalizations, particularly those that are the result of elective or previously scheduled surgery for preexisting conditions, which have not worsened after initiation of treatment, will not be classified as SAEs. For example, an admission for a drainage of obstructed bile duct would not be classified as an SAE. Pre-specified study hospitalizations for observation are not considered SAEs. All overdoses, whether or not resulting in an AE, require reporting within 24 hours.

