All Grade 3 and greater AEs and SAEs that occur after the first treatment with RT and through 4 weeks of treatment will require reporting by the investigational site. SAEs that meet the criteria for expedited reporting to the FDA will be reported in accordance with US regulations governing safety reporting (Title 21 of the Code of Federal Regulations [CFR] 312.32 and 312.33). Reporting of SAEs by the investigator to his or her Institutional Review Board (IRB) will be done in accordance with the standard operating procedures and policies of the IRB. Adequate documentation must be maintained showing that the IRB was properly notified.

In case of an SAE, the investigator will electronically report to the University of South Florida Institutional Review Board via website http://www.research.usf.edu/cs/.

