#### 8.6 SAFETY OVERSIGHT

The Protocol Monitoring Committee (PMC) monitors its assigned ongoing research protocols for adverse event reporting, data and safety monitoring, and internal audit findings. The PMC,

upon review of any agenda item, may approve the study for continuation, require revisions, or suspend or close a protocol. This study will be reviewed by the PMC for data and safety monitoring. The principal investigator will enter into Oncore all adverse events and deviations as they occur for review by the PMC.

The Principal Investigator is ultimately responsible for every aspect of the design, conduct, and actions of all members of the research team. This includes final analysis of the protocol.

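### Mandatory grade 3+ adverse-event reporting stops at week 4 of a 5–7 week radiotherapy course and disagrees with the protocol's other safety windows

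*Combined protocol and SAP*

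**What the plan says.** Two subsections stop at week 4 of radiotherapy (RT):

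- Section 8.4.1 makes these events mandatory in routine submissions, captured in OnCore: "All Grade 3 or greater Adverse Events possibly, probably, or definitely related to radiotherapy up to the primary outcome time point (4 weeks".
- Near its end, section 8.4.2 says that grade 3+ adverse events (AEs) and serious adverse events (SAEs) "that occur after the first treatment with RT and through 4 weeks of treatment will require reporting by the investigational site". It has no relatedness condition.

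The other provisions continue past week 4:

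- Section 8.3, capture: "All AEs, including local and systemic reactions not meeting the criteria for SAEs, will be captured on the appropriate CRF".
- Section 8.3, recording of reportable events from consent "until 7 (for non-serious AEs) or 30 days (for SAEs) after the last day of study participation".
- Section 8.3, after treatment: "RT-related AEs and SAEs will be collected at follow-up contact 90 days from the end of treatment", unless confounding new treatment has begun.
- Section 8.4.2, opening: a serious event that "occurs in a patient during the course of the study, irrespective of the treatment received by the patient, must be reported within 24 hours". The E2A definitions below it repeat the 24-hour rule for any SAE, related or not, and add: "It will be recorded on both the SAE form and the CRF AE page".
- Section 8.6: "The principal investigator will enter into Oncore all adverse events and deviations as they occur for review by the PMC".

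Section 8.2.2 says that the assessed relationship to treatment does not determine what is reported.

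**The concern.** Week 4 is when tumour response is measured. It is not a natural boundary for toxicity: every planned course is still running, and the final fractions and recovery lie ahead. The protocol's own intensification step, a sixth weekly fraction for conventional patients who miss the predicted reduction, also belongs mainly to that later period.

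A data manager cannot tell from the text which rule decides what must be submitted. One who follows 8.4.1 and the late sentence in 8.4.2 may stop at week 4, while one who follows 8.3 and 8.6 will continue. Non-serious grade 3+ events from late RT, acceleration and recovery could then be reported for some patients and not for others. Section 8.5 sets no halting rules, so oversight rests on the Protocol Monitoring Committee (PMC) seeing a consistent record.

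**Working it through.** **Inputs.** Section 6.1: conventional RT is 30, 33 or 35 fractions of 2 Gy, five per week. Hyperfractionation is 50, 54 or 58 fractions of 1.2 Gy, ten per week. Section 8.3: contact 90 days after the end of treatment.

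**The plan's own figure.** Section 7.1 places week 4 at about fraction 20 (conventional) or 40 (hyperfractionated). Fractions per week × 4 gives 5 × 4 = 20 and 10 × 4 = 40, so both reproduce.

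**Course length and treatment still to come.** Length = fractions ÷ fractions per week. Remaining share = (total − fractions given by week 4) ÷ total.

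| Schedule | Length (weeks) | Fractions after week 4 | Share |
|---|---|---|---|
| Conventional, 30 | 30/5 = 6.0 | 10 | 33% |
| Conventional, 33 | 33/5 = 6.6 | 13 | 39% |
| Conventional, 35 | 35/5 = 7.0 | 15 | 43% |
| Hyperfractionated, 50 | 50/10 = 5.0 | 10 | 20% |
| Hyperfractionated, 54 | 54/10 = 5.4 | 14 | 26% |
| Hyperfractionated, 58 | 58/10 = 5.8 | 18 | 31% |

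Fraction size is constant within a schedule, so these are also the shares of gross-disease dose. Every course runs 1 to 3 weeks past the limit.

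**Acceleration.** Sections 4.1 and 6.1 give neither an assessment date nor a start date. I infer week 4 because the 32% threshold is the week-4 endpoint and section 7.1 schedules imaging then.

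- If the sixth fraction starts in week 5, all accelerated treatment follows the limit. The remaining share is 33–43%, and the course ends at 4 + 10/6 = 5.7 to 4 + 15/6 = 6.5 weeks.
- If an early scan allows one sixth fraction in week 4, 21 fractions have been given. The remaining share is 9/30, 12/33 or 14/35, that is 30–40%.

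**From week 4 to the 90-day contact.**

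- Conventional: 14 + 90 = 104 to 21 + 90 = 111 days.
- Hyperfractionated: 7 + 90 = 97 to 12.6 + 90 = 102.6 days.
- Accelerated from week 5: 11.7 + 90 = 101.7 to 17.5 + 90 = 107.5 days.

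The period from RT start to that contact is 5 + 90/7 = 17.9 to 7 + 90/7 = 19.9 weeks. Four weeks cover 4/17.9 = 22% to 4/19.9 = 20% of it.

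**The rules compared.**

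- *SAEs:* the late sentence in 8.4.2 stops at week 4, while the opening of the same subsection and the E2A text run through the study.
- *Non-serious grade 3+ events:* 8.4.1 and 8.4.2 stop at week 4, while 8.3 and 8.6 do not.
- *Attribution:* 8.4.1 takes related events only, 8.4.2 takes all, and 8.2.2 says that relatedness does not decide.
- *Database:* 8.4.1 and 8.6 both place the data in OnCore, with different limits.

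**The case against.** The strongest reply is that all the rules can be met at once. Sections 8.4.1 and 8.4.2 set a minimum. Neither says that only events up to week 4 count or that later ones are to be left out. Staff who follow 8.3 and 8.6 put every event on the CRF and into OnCore and so satisfy the narrower rules too. Failing to do so would be a deviation under section 14.3. The trial has one site, and no separate submission dataset is described from which an OnCore event would be missing. No toxicity endpoint is defined, and section 10 plans no toxicity summary.

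Much of this stands. A reader might infer that serious or severe events after week 4 are lost. The documents do not support that: SAEs have study-long 24-hour reporting, and 8.3 and 8.6 cover the rest. A reader might also infer that a planned safety analysis or the efficacy conclusion is biased. No such safety analysis exists, and the response test and two-stage rule do not use these data.

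The inconsistency remains even so. Section 8.3 ties its recording window to reportable events, and 8.4.1 and 8.4.2 are where the protocol says which grade 3+ events must be reported. A mandatory minimum that ends before treatment does is poorly placed even when read as a minimum. The distinction between recording and reporting also leaves the attribution mismatch unresolved.

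**Conclusion.** The point holds as a reporting inconsistency worth correcting. The mandatory grade 3+ window ends at week 4, with 20–43% of fractions still to come and 97–111 days before the protocol's own 90-day contact. It conflicts with 8.3, with 8.6 and, for SAEs, with its own subsection. The risk is confined to inconsistent reporting of non-serious grade 3+ events after week 4, and to uncertainty over whether unrelated ones are required.

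The timing figures assume courses delivered as planned, without breaks. The statement about acceleration rests on the inferred week-4 trigger. That week 4 is a poor safety limit is a judgement, based on the remaining treatment and the protocol's own later collection. The documents give no toxicity rates or onset times, so the number of events affected cannot be computed. It could be zero if 8.3 and 8.6 are followed throughout.

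**What to change.** One amendment to the wording of sections 8.3 and 8.4:

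- **8.4.1:** delete the week-4 limit and the relatedness filter. Require all grade 3+ AEs, with attribution recorded, in OnCore from the first RT fraction to the end of the 8.3 window, including the 90-day contact.
- **8.4.2, late sentence:** delete the week-4 limit, point to the same window for grade 3+ AEs, and refer SAEs to the study-long 24-hour rule earlier in the subsection.
- **8.3:** state that CRF, OnCore and routine submissions share this one window. Recording from consent to the first fraction continues as now. Keep the proviso on confounding new treatment at the 90-day contact.

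Do not make day 90 a new cutoff. Section 8.3 already runs to 7 or 30 days after last participation, and sampling continues to 24 months.

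No new visits are needed: section 7.3 already schedules weekly evaluations during RT and visits at 4 weeks and 2–3 months, and 8.3 already requires the 90-day contact. The cost is more data entry, and possibly chart abstraction of post-week-4 grade 3+ events for patients already treated. Sample size and power do not change.
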